#### 7.3.6 Fatigue/Somnolence

Fatigue has been noted as an adverse effect of selinexor in adult studies, and more significant fatigue, accompanied by somnolence, has been noted in pediatric studies to date, potentially associated with cerebral edema. Glucocorticoid premedication continued for 48 hours post-dosing has been an effective management to date. Consideration may also be given to the use of methylphenidate (Initial: 0.3 mg/kg/dose PO qAM. Maintenance: 0.3-1 mg/kg PO qAM; maximum daily dose: 60 mg/day).

#### 7.4 **Growth Factors**

Growth factors that support platelet or white cell number or function can be used in the setting of Grade 4 neutropenia and thrombocytopenia. The Study Chair should be notified before growth factors are initiated.

#### 7.5 **Concomitant Medications**

Appropriate antibiotics, blood products, antiemetics, fluids, electrolytes and general supportive care are to be used as necessary (see [Section 7.3](#)). Clinical evidence suggests that selinexor can be safely given with acetaminophen, but given the theoretical potential for GSH depletion, acetaminophen should not be taken within 2 hours of administration of selinexor, and it is *recommended* that the total daily dose of acetaminophen should not exceed 20 mg/kg (maximum 1 gram/day) on days of selinexor dosing.

#### 7.6 **Part C (HGG Surgical Expansion Cohort)**

For HGG patients who temporarily discontinue protocol therapy to undergo scheduled tumor resection, therapy may not be restarted until wound healed (minimum 3 weeks) and until recovery to eligibility requirements ([Section 4.0](#)). Although patients will not be taking selinexor during the recovery period, platelets should be monitored as part of the twice weekly CBCs required during Cycle 1 as per [Section 8.1](#), and platelets should be maintained at a safe level to prevent post-operative bleeding as per institutional standards. Failure to adequately recover from surgery within 6 weeks after surgery will require removal from protocol therapy.

**8.0 EVALUATIONS/MATERIAL AND DATA TO BE ACCESSIONED**

**8.1 Required Clinical, Laboratory and Disease Evaluation**

All clinical and laboratory studies to determine eligibility must be performed within 7 days prior to enrollment unless otherwise indicated. Laboratory values used to assess eligibility (see [Section 4.0](#)) must be no older than seven (7) days at the start of therapy. Laboratory tests need **not** be repeated if therapy starts **within** seven (7) days of obtaining labs to assess eligibility. If a post-enrollment lab value is outside the limits of eligibility, or laboratory values are older than 7 days, then the following laboratory evaluations must be re-checked within 48 hours prior to initiating therapy: CBC with differential, bilirubin, ALT (SGPT) and serum creatinine. If the recheck is outside the limits of eligibility, the patient may not receive protocol therapy and will be considered off protocol therapy. Imaging studies must be obtained within 14 days prior to start of protocol therapy (repeat the tumor imaging if necessary).

STUDIES TO BE OBTAINED	Pre-Study	During Cycle 1	Prior to Subsequent Cycles^
History	X	Weekly	X
Physical Exam with vital signs	X	Weekly	X
Neurologic Exam	X	Weekly	X
Pregnancy Test 	X	End of Cycle 1 	Every other cycle x 2 then q 3 cycles 
Height, weight	X	Weekly	Every other week during cycles 2 and 3 then prior to each cycle
BSA	X		X
Performance Status	X		
CBC, differential, platelets	X	Twice Weekly (every 3 to 4 days) 	Weekly 
Urinalysis	X		
Electrolytes including Ca ++ , PO 4 , Mg ++	X	Weekly	X
Creatinine, ALT, AST, bilirubin	X	Weekly	X
Albumin	X		X
Amylase, Lipase	X		X
Tumor Disease Evaluation	X	End of Cycle 1 	Every other cycle x 2 then q 3 cycles 
Patient Diary 		Weekly	X
Pharmacokinetics 	X	X	
Pharmacodynamic Studies 	X	X	
Tissue Studies  (Part C)	X		
Snellen Eye Chart 	X		Every other cycle x 2 then q 3 cycles 

^ Studies may be obtained within 72 hours prior to the start of the subsequent cycle.

 Women of childbearing potential require a negative pregnancy test prior to starting treatment; sexually active patients must use two effective methods of birth control- including a medically accepted barrier method of contraceptive method (e.g., male or female condom). Abstinence is an acceptable method of birth control. Pregnancy testing is required prior to tumor imaging per institutional guidelines.

 If patients develop Grade 4 neutropenia then CBCs should be checked every 3 to 4 days until recovery to Grade 3

 Tumor Disease Evaluation should be obtained on the next consecutive cycle after initial documentation

THIS PROTOCOL IS FOR RESEARCH PURPOSES ONLY, SEE PAGE 1 FOR USAGE POLICY

- of either a PR or CR. Please note that for solid tumor patients, if the institutional investigator determines that the patient has progressed based on clinical or laboratory evidence, he/she may opt not to confirm this finding radiographically.
- 4 Patient diary (see [Appendix VII](#)) should be reviewed and uploaded into RAVE weekly during Cycle 1, and after completion of each treatment cycle.
  - 5 See [Section 8.3](#) for timing of PK studies.
  - 6 In consenting patients. See [Section 8.4](#) for timing of Pharmacodynamic studies.
  - 7 See [Section 8.5](#) for details of tissue studies.
  - 8 Part C: Observations are required as scheduled during protocol treatment only; *i.e.* weekly labs and observations are not required during the “surgery window” and may be held until resuming protocol therapy.
  - 9 Patients in Part C who interrupt treatment of Cycle 1 due to required resection should have scans repeated prior to resuming protocol therapy.
  - 10 Snellen eye chart should be used to assess visual acuity. If a decline in visual acuity occurs or other visual symptoms occur, the patient should be referred to an ophthalmologist for an examination.

## 8.2 Radiology Studies

- 8.2.1 Central Radiology Review for Response: Patients who respond (CR, PR, or MR) to therapy or have long term stable disease (SD) ( $\geq 6$  cycles) on protocol therapy will be centrally reviewed. COG Operations Center will notify the Imaging Center of any patient requiring central review. The Imaging Center will then request that the treating institution forward the requested images for central review. The central image evaluation results will be entered into RAVE for review by the COG Operations Center and for data analysis.

The images are to be forwarded electronically to the Imaging Research Center at Children’s Hospital Los Angeles via the LifeImage.

COG institutions that are not connected via the LifeImage can send the images on hard copy film, CD ROM, USB flash drive or by FTP. Submitted imaging studies should be clearly marked with the COG patient ID, study number (ADV1414) and date and shipped to [name] at the address below:

[name], CRP  
Administrator, Imaging Research Center  
Children’s Hospital Los Angeles  
[name]  
[name]  
[contact]  
[contact]  
E-mail: [contact]

## 8.3 Pharmacology (Required)

- 8.3.1 Description of Studies and Assay  
Pharmacokinetics (PK) will be performed to determine the PK of selinexor in children. Pharmacokinetic analysis will be conducted at a bioanalytical laboratory using a validated assay.

THIS PROTOCOL IS FOR RESEARCH PURPOSES ONLY, SEE PAGE 1 FOR USAGE POLICY

### 8.3.2 Sampling Schedule

Blood samples will be obtained at the time points specified in [Appendix III](#) and just before tumor resection for patients on part C.

### 8.3.3 Sample Collection and Processing Instructions

Blood samples (1 ml) will be collected in the provided Vacutainer K2EDTA tubes. (Please note the provided tubes may be larger than the required blood volume per sample so should not be filled completely). Record the exact time that the sample is drawn along with the exact time that the drug is administered.

1. Invert the tube gently at least 8 to 10 times to ensure mixing of the K2EDTA and blood.
2. Immediately after collection place K2EDTA tube on ice or at 4°C for no longer than 30 minutes.
3. Centrifuge tube within 30 minutes of collection at 2000 g for 10 minutes at 4°C until red cells and plasma are separated by a well-formed polymer barrier.
4. Transfer the plasma sample equally, using a transfer pipette, into two pre-labeled LoBind™ Eppendorf protein tubes (Aliquot A and B). *Do not transfer the Buffy coat or any of the red cell pellet into the plasma sample as this will render the sample unusable for analysis.*
  - The aliquot A sample should be  $\geq 0.2$  ml, so if total plasma sample is  $< 0.4$  ml, place most of the sample in Aliquot A.
  - **Please be sure to parafilm the tops of the Eppendorf LoBind™ Protein Tubes.**
5. Immediately after transfer of the plasma to the pre-labeled LoBind™ Eppendorf protein tubes, freeze the plasma aliquots on dry ice, snap-freeze in liquid nitrogen, or place directly into a -80°C freezer. Store samples at -80°C until shipping.

### 8.3.4 Sample Labeling

Each tube must be labeled with the study ID number, the patient ID number, the nominal time the sample was drawn, the aliquot (A or B), and a barcode ID number. All information on the PK labels is pre-printed with the exception of the patient ID number, which the site must write on each label using a fine-tip permanent marker.

Data should be recorded on the Pharmacokinetic Study Form, which must accompany the sample(s) when shipped. Record the actual collection date and time associated with the scheduled collection time point. Any handwritten changes made to the pre-printed barcode labels will not be captured when the barcodes are scanned.

THIS PROTOCOL IS FOR RESEARCH PURPOSES ONLY, SEE PAGE 1 FOR USAGE POLICY

- 8.3.5 **Sample Shipping Instructions:** Batch and ship all Aliquots A for each patient together in the same shipment on dry ice to AIT Bioscience. Note: If samples for more than 1 patient are being shipped, samples must be grouped (e.g., separate boxes or paper sleeves for each patient). Retain Aliquot B samples until requested by study assigned Research Coordinator to be shipped.

Shipment notification with tracking number should be sent to [REDACTED] [contact]; [contact]) and the study assigned Research Coordinator, along with a copy of the PK Study form.

#### 8.4 Pharmacodynamics

- 8.4.1 **Description of Studies:** Plasma proteins analysis will be performed for the identification of predictive biomarkers of response to selinexor ([Appendix IV-A](#)). Whole blood RNA will be collected for gene expression analysis using quantitative PCR ([Appendix IV-B](#)).
- 8.4.2 **Sampling Schedule**  
On cycle 1, day 1, samples will be collected pre- and 4 hours after dose is given in consenting patients.
- 8.4.3 **Sample Collection and Handling Instructions**  
Blood samples (2-2.5 ml) will be collected. Record the exact time that the sample is drawn along with the exact time that the drug is administered.
- 8.4.4 **Sample Labeling**  
Each tube must be labeled with the patient's study registration number, the study I.D., and the date and time the sample was drawn. Data should be recorded on the Correlative Study Form, which must accompany the sample(s).
- 8.4.5 **Sample Processing and Shipping Instructions:** Refer to [Appendix IV-A](#) and [Appendix IV-B](#) for sample processing and shipping details.

#### 8.5 Tissue Studies (Part C only)

Archival tumor tissue should be submitted for all patients in Part C. If a patient does not have tissue available, the study chair must be notified prior to enrollment.

##### 8.5.1 Description of Studies

Tissue will be collected from original diagnosis or most recent resection and the resection that occurs as part of Part C.

8.5.1.1 Pharmacokinetics: Levels of selinexor will be determined in the tumor as

THIS PROTOCOL IS FOR RESEARCH PURPOSES ONLY, SEE PAGE 1 FOR USAGE POLICY

well as in blood at the time of resection to calculate blood/tumor ratio.

8.5.1.2 Pharmacodynamics:

- a. Immunohistochemistry studies will be performed on fixed tumor tissue from pre-treatment and post-treatment specimens. Targets for analysis include XPO1, XPO1 cargos (p53, IKB alpha, pRb, FOXO3A, Survivin), cell cycle regulating proteins (c-Myc, Cyclin B, Cyclin D, ERK1, AKT1), and cell viability and cell death markers (H&E, Masson's trichrome, KI67, cleaved Caspase 3, TUNEL, Bcl2, Mcl1, FAS, ARRDC3, p75 NGFR).
- b. Quantitative PCR will be performed on pre- and post-treatment tumor specimens for the following: XPO1, cell viability and cell death markers (NFkB, IKB alpha, BID, PUMA, CHOP, BAX), and genes that are upregulated once XPO1 is inactivated (based on Karyopharm gene chip studies) (ARRDC3, NGFR, SLC family, PCLO).

8.5.2 Sample Collection, Handling, and Shipment

Tissue from the on-therapy resection will be preserved at the time of resection. Detailed instructions regarding collection, handling, and shipping of tissue samples are located in [Appendix V](#).

9.0 AGENT INFORMATION

9.1 **Selinexor**

(Xpovio™, KPT-330) NSC# 781780 [REDACTED]

[REDACTED]

[REDACTED]

[REDACTED]

[REDACTED]

THIS PROTOCOL IS FOR RESEARCH PURPOSES ONLY, SEE PAGE 1 FOR USAGE POLICY

[REDACTED]

[REDACTED]

[REDACTED]

[REDACTED]

[REDACTED]

[REDACTED]

[REDACTED]

[REDACTED]

[Redacted]

[Redacted]

[Redacted]

[Redacted]

[Redacted]

[Redacted]

**10.0 CRITERIA FOR REMOVAL FROM PROTOCOL THERAPY AND OFF STUDY CRITERIA**

**10.1 Criteria for Removal from Protocol Therapy**

- a) Clinical (including physical examination or serum tumor markers) or radiographic evidence of progressive disease (See [Section 12.0](#)).

THIS PROTOCOL IS FOR RESEARCH PURPOSES ONLY, SEE PAGE 1 FOR USAGE POLICY

- b) Adverse Events requiring removal from protocol therapy (See [Section 6.0](#)).
- c) Refusal of further protocol therapy by patient/parent/guardian
- d) Non-compliance that in the opinion of the investigator does not allow for ongoing participation.
- e) Completion of 24 cycles
- f) Physician determines it is not in the patient's best interest.
- g) Repeated eligibility laboratory studies (CBC with differential, bilirubin, ALT (SGPT) or serum creatinine) are outside the parameters required for eligibility prior to the start of selinexor (See [Section 8.1](#)).
- h) Failure to adequately recover from surgery within 6 weeks after surgery (patients in Part C)
- i) Study is terminated by Sponsor.
- j) Pregnancy

**Patients who are removed from protocol therapy during cycle 1 should continue to have the required observations in [Section 8.1](#) until the originally planned end of the cycle or until all adverse events have resolved per [Section 13.4.4](#), whichever happens LATER. The only exception is with documentation of the patient's withdrawal of consent. Patients who are removed from protocol therapy in subsequent cycles should have the necessary observations to ensure adequate clinical care.**

Patients who are off protocol therapy are to be followed until they meet the criteria for Off Study (see below). Ongoing adverse events, or adverse events that emerge after the patient is removed from protocol therapy, but within 30 days of the last dose of investigational agent, must be followed and reported via RAVE and CTEP-AERS (if applicable). Follow-up data will be required unless consent is withdrawn.

## 10.2 Off Study Criteria

- a) Thirty days after the last dose of the investigational agent.
- b) Death
- c) Lost to follow-up
- d) Withdrawal of consent for any further required observations or data submission.
- e) Enrollment onto another COG therapeutic (anti-cancer) study
- f) The patient does not receive protocol treatment after study enrollment

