**1.2 Secondary Aims**

- 1.2.1 To determine the antitumor effect of selinexor in a preliminary manner in children with recurrent/refractory solid and CNS tumors.
- 1.2.2 To determine the pharmacodynamic properties of selinexor in children and adolescents with refractory solid tumors in plasma proteins and whole blood RNA.
- 1.2.3 To explore the penetration, pharmacodynamic effects, and biologic effects of selinexor in tumor tissue of patients with recurrent/refractory HGG requiring resection.
- 1.2.4 To further assess the toxicity and antitumor effects of selinexor in children with recurrent/refractory HGG in expanded cohorts following dose-escalation by measuring rate of objective radiographic response (medical patients) and rate of progression-free survival (PFS) six months from the start of treatment (surgical patients).

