Accrual to Parts B and C will only open once the MTD or recommended phase 2 dose has been determined in Part A, and may open concurrently with the PK expansion described above.

A maximum of 24 patients are expected to enroll in Parts B and C combined, assuming an inevaluability rate of 20%. We anticipate that each part of the study will require 6-12 months for enrollment.

Response for Part B will be defined as either MR, PR or CR on two consecutive 2D measurements on standard imaging done 4 weeks apart (See [Section 12.6](#)). Sustained responses are very rare in this cohort of recurrent non-DIPG HGGs. We will consider the agent of sufficient interest for further evaluation in this disease category if at least one PR or CR, or at least two MRs, is observed among 10 enrolled patients. A response rate of 20% or more would be evidence of sufficient activity. If the true response rate is 20%, then the probability of observing one or more responses among 10 evaluable patients is about 89.3%. If the response rate is 5%, then the probability of observing at least one response is about 40.1%.

Clinical benefit for Part C will be evaluated separately using the criteria of no visible disease progression six months from the start of treatment. If two or more of a cohort of up to six patients are unable to resume therapy within 6 weeks after surgery, the surgical arm will be declared not feasible. If Part B has fully accrued, Part C will close to further accrual.

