### 11.5 Pharmacokinetic and Correlative Studies and Response Analysis

A descriptive analysis of pharmacokinetic (PK) parameters of selinexor will be performed to define systemic exposure, drug clearance, and other pharmacokinetic parameters. The PK parameters will be summarized with simple summary statistics, including means, medians, ranges, and standard deviations (if numbers and distribution permit).

While the primary aim of this study is to evaluate the toxicity of selinexor, patients will have disease evaluations performed as indicated in [Section 8.1](#). Disease response will be assessed according to RECIST criteria for patients with solid tumors, or the criteria specified in [Section 12.6](#) for patients with CNS tumors, and will be reported descriptively.

Clinical benefit for Part B will be defined in one of two ways, either PR or CR on two consecutive 2D measurements on standard imaging (see [Section 12.6](#)) or as > 12 weeks from first dose without progressive disease, while clinical benefit in Part C will be defined as no visible disease progression six months from the start of treatment. Clinical benefit rate will be summarized separately for each of Parts B and C with 95% confidence intervals.

All these analyses will be descriptive and exploratory and hypotheses generating in nature.

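### Part C is to be reported on progression status at six months, but required follow-up ends 30 days after the last dose, with two endpoint wordings and no rule for unknown status (minor)

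*Combined protocol and SAP*

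**What the plan says.** **Endpoint.** Aim 1.2.4 assesses surgical patients by the "rate of progression-free survival (PFS) six months from the start of treatment (surgical patients"). Section 11.1 uses a different criterion for Part C, "no visible disease progression six months from the start of treatment", and section 11.5 repeats it. Section 11.5 then commits to an estimate: "Clinical benefit rate will be summarized separately for each of Parts B and C with 95% confidence intervals". Progression-free survival is not defined in the document.

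**Follow-up.** Section 10.1 follows patients who have left protocol therapy until they meet an off-study criterion. The first criterion in section 10.2 is "Thirty days after the last dose of the investigational agent". Others are loss to follow-up, withdrawal of consent and enrollment on another COG therapeutic study. Section 10.1 also says "Follow-up data will be required unless consent is withdrawn", without a duration or an assessment.

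**Exits without imaging progression.** Section 10.1 lists adverse events, refusal, non-compliance, physician decision and failure to recover from surgery within six weeks. Its progression criterion is broader than imaging: "Clinical (including physical examination or serum tumor markers) or radiographic evidence of progressive disease".

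**Size and evaluability.** Section 11.1 plans up to 10 evaluable patients in Part C and at most 24 enrolled in Parts B and C together, allowing 20% inevaluable. It closes Part C if Part B has fully accrued. Section 11.2.3 defines evaluability for response only for patients who meet Part B eligibility.

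**The concern.** The status that Part C is meant to report lies beyond the point where required follow-up can stop. A patient who leaves treatment for toxicity, refusal or poor surgical recovery, with no progression seen, can go off study months before the endpoint date. The plan does not say whether such a patient is replaced, dropped, or counted as a success or a failure.

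The two wordings add a second ambiguity. Under progression-free survival in its usual meaning, death is a failure. Under a criterion of no visible progression, death without a progressing scan could be read either way.

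At stake is one secondary rate and its interval. With 10 patients or fewer, both depend on handling that would be chosen after the outcomes are known.

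**Working it through.** **1. The plan's own figure.** Parts B and C plan 10 + 10 = 20 evaluable patients. 20 × 1.20 = 24, which matches section 11.1 (dividing instead, 20 / 0.80 = 25). No target rate, null rate or power is given for the Part C endpoint, so there is nothing further to reproduce. An equal split, which is an assumption, gives 24 / 2 = 12 enrolled in Part C.

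**2. When follow-up covers the endpoint.** Six months is 365.25 / 2 = 182.6 days, about Day 183. Section 10.2(a) adds 30 days to the last dose, so coverage needs a last dose on or after about 183 − 30 = Day 153. Patients who stop for documented progression are known failures and are unaffected. So are patients still on treatment at about Day 153.

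**3. Patients who never resume after surgery.** Section 5.3.3 places resection after the Day 8 dose and before the Day 15 dose, and allows six weeks for recovery.
- Last dose on Day 8: 8 + 30 = Day 38, when 10.2(a) is met if read literally.
- Resection on Day 9 to 14: the recovery window closes at 9 + 42 = Day 51 to 14 + 42 = Day 56.

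The off-study criterion is thus met before the protocol has decided whether the patient failed to recover. The clock in 10.2(a) runs from the last dose, not from removal. Section 10.1 requires patients removed during Cycle 1 to continue the section 8.1 observations until the planned end of the cycle or resolution of adverse events, whichever is later. That can run past Day 38, but it is not tied to six months.

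These days depend on the number of pre-operative doses. Section 11.1 allows up to four where section 5.3.3 has two. Four weekly doses would end on Day 22, giving 22 + 30 = Day 52 for 10.2(a). If resection then fell on Day 23 to 28, the window would close on Day 65 to 70. The two sections contradict each other and must be reconciled. On either text, follow-up can end well before Day 183.

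**4. Effect on the rate.** The number of unknowns is not in the documents, so it is assumed. Each unknown moves the rate by 100/n points between being counted as failure and as success, which is 10 points at n = 10. Exact (Clopper-Pearson) limits are the 0.025 quantile of Beta(x, n − x + 1) and the 0.975 quantile of Beta(x + 1, n − x). With 3 patients known to be progression-free among 10:

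| Unknown | Counted as failures | Dropped | Counted as successes |
|---|---|---|---|
| 1 | 3/10 = 30% (6.7 to 65.2) | 3/9 = 33.3% (7.5 to 70.1) | 4/10 = 40% (12.2 to 73.8) |
| 2 | 3/10 = 30% (6.7 to 65.2) | 3/8 = 37.5% (8.5 to 75.5) | 5/10 = 50% (18.7 to 81.3) |
| 3 | 3/10 = 30% (6.7 to 65.2) | 3/7 = 42.9% (9.9 to 81.6) | 6/10 = 60% (26.2 to 87.8) |

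**5. Rules that might settle unknown status.** Section 11.2.3 classes all other patients as non-responders, but it does so for the rule on complete and partial responses among patients meeting Part B eligibility. It does not address six-month status in Part C.

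**The case against.** The strongest reply is that little depends on this. Section 11.5 calls these analyses descriptive, exploratory and hypothesis-generating. No threshold applies to the Part C rate, and the cohort exists mainly for drug-level and pharmacodynamic work on tumor tissue. The interval for 3/10 already spans 65.2 − 6.7 = 58.5 points, so one unknown changes little that a reader could conclude. The failed-recovery group is also limited: under section 11.1 the surgical arm is declared not feasible if two or more of up to six patients cannot resume within six weeks. All of this stands, and it sets the severity.

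A second reply is that other text may secure the data. Section 10.1 requires follow-up data, but the sentence opening the same paragraph ends follow-up at off study. Section 12.7.1 urges documentation of progression after discontinuation, in a note on symptomatic deterioration and with no time point. Section 14.1 refers to a separate case report form packet with a submission schedule. That packet is not among the documents and may ask for more. None of the text available sets a six-month assessment.

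A third reply narrows the gap between the wordings. Footnote 3 in section 8.1 lets only solid tumor patients skip radiographic confirmation of clinical progression, so progression of a glioma arguably needs imaging. That weakens the ambiguity for clinical progression. It does not settle death without imaging.

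A reader might also infer that scan spacing inflates the six-month rate by a calculable amount. The documents do not support this. Progression found between scheduled scans is ordinary interval censoring, the protocol never says that progression detected late counts as progression-free, and clinical examinations continue at every cycle.

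**Conclusion.** The point holds and is minor. As written, the plan commits to a six-month rate with a confidence interval while requiring no six-month status for a Part C patient who stops without progression before about Day 153. Its two wordings differ on death without imaging progression, and it has no rule for unknown status.

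The effect is confined to one secondary, descriptive rate in at most 10 evaluable patients, fewer if Part B fills first. Each unknown is worth 10 points at n = 10. That size rests on an assumed count of unknowns and an assumed 3 known successes.

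A reader might infer that outcome data will in fact be lost, or that a decision of the trial is compromised. The documents support neither. They give no count of such patients, the form schedule is not available, and no sample size, test or go/no-go rule uses this endpoint.

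**What to change.** 1. For Part C only, amend section 10.2(a) so that disease and vital status are collected from routine-care records until progression, death or six months from the first dose, with no added scan.
2. Use one definition in 1.2.4, 11.1 and 11.5: six-month progression-free survival, with progression or death as failure. State how symptomatic deterioration (12.7.1) and clinical progression (10.1(a)) are counted.
3. Put all treated Part C patients in the denominator, report the number with unknown status, and give the rate with unknowns counted as failures and as successes.

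Separately, sections 5.3.3 and 11.1 must be reconciled on the number of pre-operative doses.

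The cost is one amendment, one status form for about 12 patients, and slightly longer passive follow-up for families who have stopped treatment. No sample size changes. Routine records do not guarantee a scan near six months, and patients who are lost, withdraw consent or join another COG therapeutic study may still be unknown. The two-way reporting in item 3 is therefore still needed.
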